Intervention	Safety Assessment	Intervention	Safety Assessment	Safety Assessment	Safety Assessment
--------------	-------------------	--------------	-------------------	-------------------	-------------------

iii. Study Design

- a. The study will comprise of a double blinded, crossover study where the subjects will serve as their own controls. There will be no medication changes made to Parkinson's disease medications throughout the subjects' participation in the study.
- b. **Randomization:** Determined by the IDS Pharmacy at UNC using a computer-generated algorithm which will determine whether subject's first intervention will be sham saline injections versus onabotulinum toxin A. The IDS Pharmacy will keep track of which agent was administered first to avoid administering same intervention twice.
- c. **Blinding:** Double-blinded study whereby the subject, the movement disorder specialist injecting neurotoxin, and the movement disorder specialist rating the patient will be unaware of the solution injected and/or planned for injection same day. To ensure that the injecting specialist is blinded to the solution, syringes will be premixed by the IDS Pharmacy and de-identified of any possible labels that would indicate the properties of the solution being administered to the subject.

Injection Sequence	Visit 1	Visit 3
Sequence AB	Botox	Placebo
Sequence BA	Placebo	Botox

- d. **Deciding between bilateral tremors:** The side to be studied shall be the limb with the tremor of greatest amplitude. This will be determined by a combination of factors: Participant self-report of which tremor is "worse", which tremor is "more disabling", as well direct observation by the examiner and the MDS-UPDRS tremor subscore per limb to determine which limb has the tremor of greatest amplitude. Once that limb is chosen, it shall be utilized throughout the duration of the study.

e. Visit 1: Day 0

- a. Screening, as per "Eligibility Criteria"
 - i. Participant will be asked to come to clinic at the time they are due for their next dose of anti-Parkinsonian medication. If they are not taking anti-Parkinsonian medication, a single dose of carbidopa/levodopa 25/100mg 1 tablet will be administered (this assumes participant meets exclusion criteria "b"). They will only take medication when instructed. Then at peak-dose effect of the medication taken:
- b. Baseline MDS-UPDRS tremor subscore obtained by movement disorder specialist

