- a. Participant will be asked to come to clinic at the time they are due for their next dose of anti-Parkinsonian medication. If they are not taking anti-Parkinsonian medication, a single dose of carbidopa/levodopa 25/100mg 1 tablet will be administered. They will only take medication when instructed. Then at peak-dose effect of the medication taken:
- b. Repeat MDS-UPDRS tremor subscore obtained by movement disorder specialist
- c. Repeat muscle strength assessment of limb: using MRC muscle testing via physical examination
- d. Repeat ARAT score obtained by occupational therapist
- e. The Px1 will be used to obtain information regarding the direction of oscillation, average amplitude, peak amplitude, and frequency of the tremor.

- f. Based on enrollment randomization from Visit 1, and after all above measures have been obtained:
 - i. If sham injection was performed at Visit 1, then onabotulinum toxin injection is performed at Visit 3 and vice versa. The same injection paradigm used in Visit 1 will be used for Visit 3 to ensure greatest level of consistency between injections.
 - g. Patient will complete a daily diary of symptoms for 30 days starting the day AFTER the study visit, to be collected by study personnel at the following study visit. The diary includes subjective assessments of tremor severity, tremor persistence, arm weakness, and arm dysfunction.
- h. **Visit 4: Day 120 (+/- 6 days per visit)**
 - a. Participant will be asked to come to clinic at the time they are due for their next dose of anti-Parkinsonian medication. If they are not taking anti-Parkinsonian medication, a single dose of carbidopa/levodopa 25/100mg 1 tablet will be administered. They will only take medication when instructed. Then at peak-dose effect of the medication taken:
 - b. Repeat MDS-UPDRS tremor subscore obtained by movement disorder specialist
 - c. Repeat muscle strength assessment of limb: using MRC muscle testing via physical examination
 - d. Repeat ARAT score obtained by occupational therapist
 - e. The Px1 will be used to obtain information regarding the direction of oscillation, average amplitude, peak amplitude, and frequency of the tremor to then be compared to Visit 3.
 - f. Patient will complete a daily diary of symptoms for 30 days starting the day AFTER the study visit, to be collected by study personnel at the following study visit. The diary includes subjective assessments of tremor severity, tremor persistence, arm weakness, and arm dysfunction.

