No power calculation can be performed. This is a pilot feasibility study to determine if onabotulinumtoxin A can be utilized to reduce resting tremor amplitude and improve arm function.

Data Analysis (Performed by [name], PhD)

Note that all statistical analysis, and as such any missing data/values/dropouts, will be performed assuming an intention-to-treat principle. All statistical estimates will be tabulated along with corresponding confidence intervals (CIs). All hypothesis tests that are observed to be not statistically significant will be reported as being inconclusive. Lastly, all data acquired for Visit 5 will be utilized for review of safety. This is to ensure that the expected washout effect is occurring and that there is expected normalization of values trending towards or back to previous baseline values. For this reason, there is an absence of any testing with the Px1 on Visit 5 (since data will not be utilized to compare to previous visits for purposes of statistical analysis).

Specific Aim 1a. The change in tremor severity effected by onabotulinumtoxin A will be compared to the change effected by sham saline. Tremor severity will be measured via the MDS-UPDRS tremor subscore. A Student's t-test will be utilized to compare postintervention measures within subjects.

Specific Aim 1b. The change in limb function as measured by the ARAT created by onabotulinumtoxin A will be compared to the change created by sham saline. A Student's t-test analysis will be used to compare change in ARAT scores within subjects.

Specific Aim 2. The strength of the correlation between MDS-UPDRS tremor subscore and tremor characteristics as assessed by the Px1 will be obtained. Will then evaluate the strength of the correlation between the change in MDS-UPDRS score and change in the ARAT score. This latter correlation will then be compared to the correlation between the change in tremor characteristics as assessed by the Px1 and the change in the ARAT score.

Specific Aim 3. Pilot data will be reviewed and trends analyzed. Subsequent power analysis will be performed to determine size of study population that is necessary to adequately measure statistically significant effect. Data regarding dropout rates will also be reviewed to determine if study methodology needs to be adjusted for a larger study population.

Interpretation of Results

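### Aims 1a and 1b name a within-subject t-test for an AB/BA crossover with no period term and no stated blocking; blocking 8:8 and adding a period term is a minor, cheap improvement

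*Combined protocol and SAP*

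**What the plan says.** Section IV.iii (Study Design) sets out sequences AB and BA. The investigational pharmacy allocates "using a computer-generated algorithm which will determine whether" toxin or saline comes first, and the Visit 3 paragraph completes the crossover: "If sham injection was performed at Visit 1, then onabotulinum toxin injection is performed at Visit 3 and vice versa". No ratio, block size or equal-sequence constraint is given. Section III.i explains the even total of 16 by cost.

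Section VI (Data Analysis) gives the tests:

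- **Aim 1a, comparison:** "The change in tremor severity effected by onabotulinumtoxin A will be compared to the change effected by sham saline".
- **Aim 1a, test:** "t-test will be utilized to compare postintervention measures within subjects".
- **Aim 1b:** "t-test analysis will be used to compare change in ARAT scores within subjects".
- **Aim 3:** "Subsequent power analysis will be performed to determine size of study population that is necessary".

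Visit 5 is kept for safety, "since data will not be utilized to compare to previous visits for purposes of statistical analysis". No section mentions a period effect, a sequence term or a crossover model. Alpha, SD, effect size and power are not stated.

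**The concern.** Let D be a participant's toxin-minus-sham difference. In sequence AB toxin comes first, so D carries the period effect with a minus sign; in BA it carries it with a plus sign. A paired t-test on D pools the two. With equal sequences the period effect cancels from the mean but stays in the variance. With unequal sequences part of it also remains in the mean, as a bias conditional on the realised split.

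The estimates and intervals are meant as preliminary data for grant proposals (Section VI, Interpretation of Results), and the pilot data feed the Aim 3 sample-size work. A period effect left in the SD would pass into both. The remedy is nearly free, which is why the point is worth raising although the trial is an unpowered pilot.

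**Working it through.** **Inputs.** From the documents: 16 participants, two sequences, one injection per period, a within-subject t-test. Assumed because not given: two-sided alpha 0.05, 16 completers, effect tau = 0.75 SD_D, and a period effect pi (period 2 minus period 1 shift) from 0 to 1 SD_D. The plan has no power figure to reproduce.

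**Model**, in units of SD_D: mean of D is tau − pi in AB and tau + pi in BA, with SD 1 within a sequence.

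*Paired t-test (plan as read), 15 df.*
- Conditional bias = pi × (n_BA − n_AB)/16. At 11:5 with pi = 0.25 this is 0.25 × 6/16 = 0.09 in absolute value.
- Expected variance = 1 + pi² × 4·n_AB·n_BA/(16 × 15), which at 8:8 is 1 + pi² × 16/15.
- With pi = 0 the noncentrality is 0.75 × √16 = 3.0, giving power 80.1%.

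*Period-adjusted test* (two-sample t-test of period differences by sequence), 14 df.
- SE = 0.5 × √(1/n_AB + 1/n_BA), which at 8:8 is 0.25.
- Noncentrality is 0.75/0.25 = 3.0, giving power 79.7% whatever pi is.

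**Break-even on interval width at 8:8.** The critical values are 2.131 (15 df) and 2.145 (14 df), ratio 1.00626. Setting √(1 + pi² × 16/15) = 1.00626 gives pi² = (1.00626² − 1) × 15/16 = 0.0118, so pi = 0.108. On power, break-even is 0.114 against the paired test at 8:8 and about 0.10 against the paired test under simple randomisation.

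**Size by period effect** (simple randomisation is itself an assumption, since the scheme is not stated):

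| pi (SD_D) | Paired CI / adjusted CI, both 8:8 | Variance inflation, 8:8 | Power, paired, 8:8 | Power, paired, simple randomisation | Power, adjusted, 8:8 |
|---|---|---|---|---|---|
| 0 | 0.994 | 1.00 | 80.1% | 80.1% | 79.7% |
| 0.1 | 0.999 | 1.01 | 79.8% | 79.7% | 79.7% |
| 0.25 | 1.026 | 1.07 | 78.1% | 77.6% | 79.7% |
| 0.5 | 1.12 | 1.27 | 72.2% | 70.8% | 79.7% |
| 1.0 | 1.43 | 2.07 | 49.1% | 50.1% | 79.7% |

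Averaged over simple randomisation, the paired test's type I error is 5.0% to 5.1% throughout.

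**Period term without blocking.** Simple randomisation gives exactly 8:8 with probability 19.6%, and 11:5 or worse with probability 21.0%. The adjusted SE grows by 3% at 10:6 and 8% at 11:5. Average adjusted power is 76.8%, and break-even rises to about 0.29 SD_D.

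**Dropout.** With 8:6 completers and pi = 0, power is 72.3% adjusted against 73.7% paired. The width break-even becomes 0.19, from (2.179 × 0.5 × √(1/8 + 1/6)) / (2.160/√14) = 1.019 and pi² = (1.019² − 1) × (14 × 13)/(4 × 8 × 6).

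**How large might pi be?** Inclusion criterion 4 requires tremor of at least 3 cm, and the visit table puts screening and baseline together at Visit 1. If Aim 1a analyses change, regression to the mean then enters period 1 only. Simulating four equally correlated visits with selection at Visit 1, and assuming 90%, 80% or 50% of those screened pass:
- Correlation 0.5: pi = 0.07, 0.13, 0.30 SD_D.
- Correlation 0.8: pi = 0.04, 0.08, 0.18 SD_D.

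If Visit 2 and Visit 4 values are compared instead, the same model gives 0.00. Over 0.04 to 0.30 SD_D the plan as read has 80.0% down to 76.7% power, against 79.7% for the fix: a 0.3-point loss to about a 3-point gain.

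**The case against.** The strongest reply is that any harm is hypothetical, and much of that stands.

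- **The design limits a period effect.** "There will be no medication changes made to" Parkinson's disease drugs, assessment is timed to peak drug effect at each visit, the injection paradigm is the same in both periods, and Visit 3 supplies a new baseline.
- **The documented source is narrow.** Regression to the mean needs Aim 1a to analyse change, whereas its test sentence speaks of post-intervention values. It needs screening to coincide with baseline, yet Section IV.i allows the first study visit on another day. It is not shown for ARAT, on which nobody is selected; there only a practice effect that fades over visits would count.
- **The range leans high.** The simulation selects on the outcome itself, but entry rests on judged amplitude and the outcome is the MDS-UPDRS subscore. With an assumed correlation of 0.8 or 0.6 between them, the top value falls to 0.23 or 0.17. In the other direction, with bilateral tremor the limb is chosen partly on that subscore, which adds some selection not quantified here.
- **The wording does not exclude the better test.** The adjusted analysis is also a Student's t-test on within-subject differences, and the pharmacy may block anyway.

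These points settle the priority. They do not remove the case for stating which test is meant and how sequence is allocated. A reader might infer that the planned test is invalid or its estimate biased. The documents do not support that: averaged over randomisation, bias is zero and type I error is nominal.

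**Conclusion.** The point holds as a minor, cheap improvement. The plan names no period term and states no blocking. A blocked 8:8 list with a period term protects against a period effect above about 0.1 SD_D, at a cost of about 0.4 power points if there is none. This rests on two-sided alpha 0.05, 16 completers and pi defined as the period 2 minus period 1 shift. At alpha 0.01 the 8:8 width break-even is 0.139, and with 8:6 completers at alpha 0.05 it is about 0.19.

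Whether the threshold is passed is unknown. The one source tied to the documents spans it (0.04 to 0.30 SD_D) on assumed inputs. A reader might take the 0.5 and 1.0 rows as forecasts of lost power; nothing in the documents points to period effects of that size, and they are sensitivity values only. The effect on Aim 3 is also small against sampling error: variance inflation is 1.07 at 0.25 SD_D, while the 95% interval for a variance on 14 df already runs from 0.54 to 2.49 times the estimate.

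**What to change.** Make one package of changes.

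1. State that the pharmacy list uses permuted blocks giving 8 participants per sequence.
2. Fix one Aim 1a outcome in advance: either Visit 2 and Visit 4 post-intervention values (no regression to the mean from Visit 1 selection under equal between-visit correlation), or within-period change (Visit 2 minus Visit 1, Visit 4 minus Visit 3). For Aim 1b keep within-period change.
3. Analyse one value per participant per period with treatment, period and sequence fixed and participant random. With complete data this is the two-sample t-test of period differences by sequence, 14 df.
4. Give Aim 3 the pooled within-sequence SD of the within-subject difference, which is √2 times the model's residual SD. Use Visit 3 only as the period 2 baseline, and keep Visit 5 for safety.

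The cost is SAP wording and a list setting, with no added visits or participants. The period term should not be adopted without blocking, for the reason shown by the 76.8% figure. Uneven dropout can undo part of the gain. Carryover is a separate matter that this change does not repair.

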When choosing the proper targets for injection of botulinum toxins in rest tremor, without proper planning one could easily overdose the muscles and lead to weakness which may outweigh the benefits on reduced tremor amplitude. To date, studies which have evaluated the effect of botulinum toxin on rest tremor in Parkinson's disease have used typical doses effective for dystonia, later titrating doses higher to effect. Given that statistically-significant effect is based on gross characterization of tremor amplitude into previously-existing nominal scales (namely the Unified Parkinson's Disease Rating Scale tremor subscore), it would not be surprising that titrating doses "to effect" will subject the participant to higher toxin doses that, in turn, are more likely to produce clinically-evident weakness. Subsequently, these same studies have not been able to correlate reduced tremor amplitude to any clear functional improvement save for a single, recently-published open-label study on the subject. However, functional improvement in the

studies has generally only been assessed through subjective, self-reported measures/scales and not through any objective measures.

We propose there is a lesson to learn from task-specific dystonias: usually we have to utilize much lower doses of botulinum toxin in practice to avoid weakness while still providing benefit on function of the limb as measured by their ability to perform the task. Given that rest tremor inherently is not related to nor produced by increased tone, there is reason to believe that low doses of botulinum toxin may still provide reduction of amplitude without inducing weakness. Previous studies sometimes injected only involve either a set of flexor or extensor muscles while others injected a combination of both muscles involved in creating the oscillatory movement. To help reduce chances of weakness as best possible, we propose that splitting doses of botulinum injections into a combination of both flexor and extensor muscles would be safest. What remains to be seen is whether such low doses of botulinum toxin injected into a combination to both tremor-inducing flexor and extensor muscles might also lead to improvement of tremor amplitude and/or function of the limb.

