 - a. Severity/Amplitude: As measured by the MDS-UPDRS tremor subscore.
 - b. Limb function: As measured by the Action Research Arm Test (ARAT)
2. Evaluate Px1 versus expert clinical assessment and its sensitivity to detect changes based on the MDS-UPDRS tremor subscore
3. Determine whether methodology for this pilot project can feasibly be applied to a larger subsequent study that could be adequately powered to detect a clinically-meaningful effect of onabotulinumtoxin A on medically-refractory rest tremor.

ii. **Hypotheses:**

1. (A) Onabotulinumtoxin A significantly attenuates the amplitude of medically-refractory rest tremor of the upper limb in Parkinson's patients as compared to sham injections; as measured by reduction in the MDS-UPDRS tremor subscore.
1. (B) Onabotulinumtoxin A significantly improves the limb function of Parkinson's patients with medically-refractory rest tremor of the upper limb as compared to sham injections; as measured by an increase in ARAT scores.

III. Subjects

i. **Pilot group**

- **Number – 16**
 - Due to the limitations brought on by internal funding for this pilot project and the overall cost of botulinum toxin, an even number of patients was chosen after a cost analysis was completed. It was determined that we could cover the cost of 16 participants throughout the proposed course of the study.
- **Gender** – male or female
- **Ethnicity** – all, no restrictions
- **Race** – all, no restrictions
- **Age** – 45-80

ii. **Eligibility Criteria**

Inclusion Criteria:

1. At least 45 years of age, and no more than 80 years of age.
2. Meet UK Parkinson's disease brain bank diagnostic criteria
3. Have clinical evidence of rest tremor of one or both upper extremities defined as involuntary, rhythmic oscillations about any joint within the upper extremities
4. Rest tremor amplitude must be at minimum 3 cm as determined by expert opinion by a movement disorders specialist. Confirmation of amplitude measurement will

be obtained from the Px1 prior to active participation in the study but will not be used for inclusion/exclusion in study participation.

5. Rest tremor must be historically refractory to at least 2 categories of medications typically used as anti-parkinsonian agents including levodopa formulations, dopamine agonists, amantadine, and anticholinergics.
6. **Determining Medication Refractoriness:**

AFTER patient is consented:

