Specific Aim 2. A statistically-significant correlation between the MDS-UPDRS tremor subscores and the tremor amplitude measurements derived from the Px1 could serve to validate this tool against the current gold standard (i.e. the MDS-UPDRS) for measuring severity of tremor in Parkinson's disease both in research and clinical practice. This preliminary data would be used for future grant proposals for larger, more rigorous studies; including potentially additional studies using the Px1 as a potentially more-sensitive measure of tremor severity/amplitude in place of the MDS-UPDRS tremor subscore. Failure to demonstrate this correlation would suggest one or more of several possibilities: (1) that the Px1 is not sufficiently accurate in its measurement acquisition algorithm, and/or (2) the MDS-UPDRS tremor subscore is subject to too much subjectivity from the rater's perception on direct visualization and has less intrarater reliability than was previously perceived. The information gathered from this pilot project could then be utilized to (1) adjust the measurement algorithm for the Px1 to improve accuracy when measuring hand movements in real-life subjects versus calibrated limbs, and/or (2) increase the number of MDS-UPDRS raters assessing a limb tremor. Using these variables, a subsequent study could be designed.

Data Storage & Security/Confidentiality/Sharing

In order to maintain privacy and confidentiality regarding subject participation, there will only be one printed copy of a spreadsheet with codes linked to their identifiers (which will only include name and date of birth). This spreadsheet will be kept in the [name] office within a locked

cabinet with multiple layers of physical security to enter this office including necessary UNC employee badge access. Once the study has ended, only codes shall remain, and the aforementioned spreadsheet shall be destroyed in a HIPAA-compliant fashion. This will not directly affect any UNC medical records.

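### Aim 2 includes Px1's sensitivity to change judged by the MDS-UPDRS tremor subscore, but the plan never relates the two instruments' changes directly and does not say how the change results will be read

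*Combined protocol and SAP*

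**What the plan says.** Section II.i gives Aim 2 two parts: how Px1 compares with expert clinical assessment, and "its sensitivity to detect changes based on the MDS-UPDRS tremor subscore".

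Section VI, Data Analysis, lists three correlations for this aim:

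1. The MDS-UPDRS tremor subscore with Px1 tremor characteristics. Neither change nor visit is mentioned.
2. "the correlation between the change in MDS-UPDRS score and change in the ARAT score".
3. Px1 change with ARAT change, to be set beside the second: "This latter correlation will then be compared to the correlation between the change in tremor characteristics as assessed by the Px1" and ARAT change.

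Two general rules in the same section apply: "All statistical estimates will be tabulated along with corresponding confidence intervals", and "All hypothesis tests that are observed to be not statistically significant will be reported as being inconclusive".

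Under Interpretation of Results, Aim 2, a significant score correlation "could serve to validate this tool against the current gold standard (i.e. the MDS-UPDRS) for measuring severity of tremor". The same paragraph says what a failed score correlation might mean and what could follow from it. It also looks ahead to later work, "including potentially additional studies using the Px1 as a potentially more-sensitive measure of tremor severity/amplitude in place of the MDS-UPDRS tremor subscore". It gives no reading of either change correlation or of their comparison.

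**The concern.** The second part of the aim is about change, and its most natural reading takes the subscore as the reference. The direct evidence would be whether Px1 moves when the subscore moves, and the plan does not list that pairing. It offers a score correlation, which mixes differences between people with movement within a person, and two correlations with a third measure, ARAT. Section VIII says that ARAT has not previously been used to assess rest tremor.

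At stake is what the pilot can pass on. The plan foresees, in hedged terms, proposals in which Px1 might replace the subscore. If the analysis is followed as written, those proposals would have no direct estimate of whether the two instruments move together, although both are recorded at Visits 1 to 4.

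**Working it through.** The documents give no target correlation, power or alpha, so there is no stated figure to reproduce. From the documents: n = 16 (section III) and both measures at Visits 1 to 4 (section IV.iii). All correlations, variance shares and the two-sided 0.05 level below are assumptions.

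**1. What a score correlation says about change.** Let s be the share of variance that is stable between people (equal in both instruments), rB the between-person correlation and rW the within-person correlation, with visit deviations independent over time. Then

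score r = s × rB + (1 − s) × rW,

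and the correlation of changes equals rW. Fix the single-visit score r at 0.6 and solve rW = (0.6 − s × rB) / (1 − s):

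| s | rB | rW (change correlation) |
|---|---|---|
| 0.7 | 0.85 | (0.6 − 0.595) / 0.3 = 0.02 |
| 0.7 | 0.50 | (0.6 − 0.35) / 0.3 = 0.83 |
| 0.5 | 1.00 | (0.6 − 0.5) / 0.5 = 0.20 |
| 0.5 | 0.40 | (0.6 − 0.2) / 0.5 = 0.80 |

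With n = 16 the critical |r| is 0.497. By simulation, the single-visit score test is significant in 73% to 74% of trials in every row, so its result does not distinguish them.

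The plan does not say which visits enter the score correlation. If four visits are averaged, it becomes [s × rB + (1 − s) × rW / 4] / [s + (1 − s) / 4]. In row order this gives 0.77, 0.53, 0.84 and 0.48, significant in about 97%, 60%, 99% and 49% of trials. Under these assumptions the test succeeds more often where the instruments' changes hardly agree.

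**2. What the ARAT route says about it.** If each change correlates r with ARAT change, and p is the partial correlation of the two changes given ARAT change, the direct correlation is r² + p(1 − r²). At r = 0.4:

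- p = 0 gives 0.16.
- p = 0.8 gives 0.16 + 0.8 × 0.84 = 0.83.

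With p unrestricted (−1 to 1), the limits at r = 0.5 are 0.25 − 0.75 = −0.50 and 0.25 + 0.75 = 1.00. Two equal ARAT correlations therefore leave the direct one largely open.

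**3. Precision of the direct estimate.** Fisher z, observed r = 0.5: atanh(0.5) = 0.549.

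- One pair per participant: SE = 1/√13 = 0.277; 0.549 ± 0.544 transforms back to 0.01 to 0.80.
- Two independent periods (best case): SE = 1/√26 = 0.196; 0.549 ± 0.384 transforms back to 0.16 to 0.73.

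**4. Ceiling from a coarse scale.** Suppose the scale is scored in whole points and true change has an SD of 0.25, 0.5 or 1.0 points. By simulation, rounding at both visits limits a perfect instrument's correlation with recorded change to 0.56, 0.78 or 0.93. The share of participants with no recorded change is 80%, 61% or 37%.

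**The case against.** The strongest defence is that the ARAT route is a reasoned choice. The background section criticises reliance on "gross characterization of tremor amplitude into previously-existing nominal scales" and presents camera measurement as the more sensitive method. If the subscore is coarse, its own change is a poor yardstick and an external functional anchor is defensible. That stands as a reason to keep the ARAT comparison. It does not supply the pairing that the aim's wording most naturally calls for, although that wording is loose.

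The added correlation is also one-sided: a high value supports Px1, while a low one may only reflect the scale. That stands too, so the estimate is supportive evidence and not a test that Px1 could fail.

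Third, this is a small pilot with hedged claims, and the correlation could be added later from the same data. True, but naming it now costs almost nothing and avoids choosing among Px1 measures after seeing results.

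A reader might infer more than the documents support:

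- *The plan ignores change.* It does not. It analyses change through ARAT, and the visit schedule compares Px1 at Visits 2 and 4 with Visits 1 and 3.
- *The plan would declare Px1 valid for change, or more sensitive, from the score correlation.* Its wording is limited to severity, and greater sensitivity appears only as a possibility for future studies.
- *The efficacy results are affected.* Px1 decides no eligibility (section III, inclusion criterion 4) and enters no Aim 1 test.

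**Conclusion.** The gap is real and confined to Aim 2. The plan contains no analysis relating Px1 change to subscore change and no reading of the change results it does plan. The general promises of confidence intervals and of an inconclusive label apply to whatever is estimated and do not fill the gap.

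That the pairing is missing can be read directly from the text and needs no assumption. The figures do rest on assumptions: a score correlation of 0.6 with a change correlation of 0.02 to 0.83 shows what is possible under the stated variance shares and does not predict this trial. Nor would the direct correlation settle which instrument is more sensitive. It shows only whether they move together. A correction is worth making because it is cheap, not because a main conclusion is at risk.

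**What to change.** In section VI, Data Analysis, Aim 2, add the within-period correlation of Px1 amplitude change with MDS-UPDRS tremor subscore change: Visit 2 minus Visit 1, and Visit 4 minus Visit 3. Give a confidence interval that allows for two periods per participant, for example by averaging the two Fisher-z values and resampling participants.

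Name one Px1 amplitude summary in advance. The visit schedule offers average and peak amplitude. Section IV.iii.l averages three measurements per visit, while section V (The Px1) describes three postures. Build the summary on the planned average, and state how the three measurements relate to the three postures.

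Keep the ARAT comparison as complementary evidence.

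In Interpretation of Results, Aim 2, state that:

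- a significant score correlation supports Px1 as a measure of severity only;
- any statement on sensitivity to change rests on the change estimates and their intervals;
- a low or imprecise value is inconclusive.

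The cost is a few sentences and a few lines of analysis, with no new data or visits. The downside is an imprecise estimate that a coarse scale can pull down even if Px1 is sensitive, so a low value should not be held against the device.
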